STUDY IDENTIFICATION

Project title	Open trial of median nerve stimulation for treatment of Tourette syndrome
Short title	Open-label MNS
NCT number	NCT05016765
IRB	Washington University Human Research Protection Office
IRB title	Open trial of median nerve stimulation for treatment of Tourette syndrome
IRB ID #	202109160
Grant support	Department funding
Grant title	n/a
IDE status	Non-significant risk device study. FDA-cleared device, 501(k) premarket notification number K080661 .
Protocol version (revision date)	Version 20220304 (March 04, 2022)

OBJECTIVES

Chronic tic disorders (CTD), including Tourette syndrome (TS), are associated with a substantially reduced quality of life [1]. Medication treatments are no more than 50-60% effective in RCTs, and are often discontinued due to unacceptable side effects [2]. Behavioral therapies require ability to participate in therapy and a specially trained therapist [3], but weekly visits to psychologists are impractical for many Americans, especially in rural areas [4]. Patients strongly desire new treatment options [5].

Here we propose (a) to determine the real-world usage and apparent utility of stimulation in people with chronic tics, and (b) to determine momentary self-rated efficacy and side effects of stimulation. In addition, we will compare results from this study to those from the "Peripheral induction of inhibitory brain circuits to treat Tourette's: pilot" study, from which participants will be drawn, in order to compare laboratory and real-world efficacy.

Aim 1. Determine the real-world usage and apparent utility of stimulation in people with chronic tics. Participants will be allowed to choose when and for how long to use the stimulation, thus reflecting how patients would use the stimulation in their daily lives outside of a research study.

Aim 2. Determine momentary self-rated efficacy and side effects of stimulation, using surveys taken at the beginning and end of stimulation periods, as well as twice daily when prompted.

Aim 3. Compare results of this trial with those from "Peripheral induction of inhibitory brain

circuits to treat Tourette's: pilot." Participants in this study are drawn from completers of the "peripheral induction" blinded RCT, allowing for clear comparisons between the laboratory conditions of the first study and the real-world conditions of the second.

Completion of these Aims will provide practical information that can inform a future, controlled clinical trial of chronic MNS delivered by a portable device.

STUDY DESIGN

Overall study timeline

The study will complete enrollment within 11 months and complete all human subjects procedures within 1 year.

Overview of each subject's participation

First we screen potential participants to ensure they meet criteria for study enrollment. All participants will be drawn from completers of the study "Peripheral induction of inhibitory brain circuits to treat Tourette's: pilot," and we will draw much of the demographic and clinical information from the RCT. Participants will attend one session (whenever possible, in person at the same visit as the final study visit for the RCT), in which they will learn how to use the device and have it set to appropriate settings. They will then take the device home to use for four weeks, during which time they will fill out brief surveys whenever they turn the device on and off, as well as at two other points throughout the day. These surveys record tic intensity and frequency, as well as discomfort due to the device. Participants will also complete a more extensive survey at the conclusion of the study.

Recruitment

Participants will be recruited from completers of the study "Peripheral induction of inhibitory brain circuits to treat Tourette's: pilot."

First visit

1. We present an informed consent document to participants (to parents of potential child participants) explaining the study, risks and benefits of participation and that participation is voluntary. The ICD will be provided online prior to the initial visit. Potential subjects will review the informed consent document with the investigator or designee and will have opportunity to resolve questions or concerns. Adult participants will provide their own informed consent. For child participants, consent from one parent or guardian is sufficient, as the study is minimal risk. Children must assent to participate.
2. All data from the "Peripheral induction of inhibitory brain circuits to treat Tourette's: pilot" study will be imported for comparison with information collected during this study.
3. If more than 2 weeks have elapsed since the most recent administration of the Adult Tic Questionnaire (ATQ) [8,9], participants will be asked to repeat it.
4. Explain use of the TENS unit, including which settings may be changed by the participant and which settings should remain on the settings established by the investigator.

5. Attach electrodes.
6. Determine stimulation threshold (12 Hz, pulse width 200μs), starting at 0 and increasing slowly until a twitch of the thumb is seen.
7. Verify that the participant is able to set up and turn on the device on their own.

Online during study period

1. Participants will complete online measures at the following times:
 - a. Turning on the stimulator
 - i. Tic intensity
 - ii. Tic frequency
 - b. Turning off the stimulator
 - i. Tic intensity
 - ii. Tic frequency
 - iii. Discomfort from stimulation
 - iv. Overall symptom improvement

Texts will be sent twice daily at predetermined times, and the participant will respond with times “c.” or “d.” below depending on stimulator use when the text is received:

- c. Answering a text, stimulator currently on
 - i. Tic intensity
 - ii. Tic frequency
 - iii. Discomfort from stimulation
 - iv. Overall symptom improvement
 - d. Answering a text, stimulator currently off
 - i. Tic intensity
 - ii. Tic frequency
2. Participants may be contacted throughout the study for reminders regarding compliance or assistance in troubleshooting issues with the device or surveys.

Online at conclusion of study

1. The study concludes 4 weeks (± 5 days) after the initial visit (or earlier, if the participant decides to stop treatment before 4 weeks).
2. We review the online questionnaires and collect the following additional measures:
 - a. Current symptom status
 - i. Adult Tic Questionnaire (ATQ) tic rating
 - ii. Premonitory Urge for Tics Scale (PUTS) [10]
 - b. Treatment efficacy and side effects
 - i. [Modified Clinical Global Impression – Efficacy Index](#)
 - ii. Patient perception of duration of improvement after stimulation
 - iii. Patient’s plans to continue using device
 - c. Open-ended comments
 - i. On device
 - ii. On study

Subject Payments

Participants will be given the TENS unit to keep at the successful conclusion of the study, a value of approximately \$30, to compensate for their loss of time.

Clinical vs. research purposes

The actual treatment with MNS is for clinical purposes and will be controlled by the participant. All other procedures in this study are done for research purposes.

POTENTIAL RISKS

(The language below, in this section, is addressed to the patient, as in an informed consent document.)

You may experience one or more of the risks indicated below from being in this study. In addition to these, there may be other unknown risks, or risks that we did not anticipate, associated with being in this study. You will be told of any new information that may affect your willingness to participate in this study. [name] will answer any questions you have about these risks.

MNS

Likely:

- Discomfort in the forearm, wrist or hand during active stimulation
- Mild skin irritation from applying or removing the surface electrodes

Other study procedures

Likely:

- The questionnaires may be slightly boring, fatiguing or challenging.

Rare:

- Some participants may be sensitive to components of the electrode pads and develop a rash where the pads are affixed to the skin. If this happens, stop using the device and contact us.
- The questions that you are asked during this study could make you feel uncomfortable. If any question makes you feel uncomfortable, you may choose not to answer it.
- Confidential information about you may be accidentally disclosed. However, we think the risk of accidental disclosure is small. The information we gather during the course of the study is coded only by a study number and is kept separately from your name, address, etc. The exception is that your phone number will be shared with Twilio.com, the text services provider we contract with.

LOCATIONS / SITES OF STUDY

Data collection: Washington University in St. Louis, and participant's location when answering surveys

Data analysis: Washington University in St. Louis

STUDY DURATION

Anticipated duration of entire research activity per participant:

- 4 weeks

Anticipated duration of entire research activity:

One year

SAMPLE SIZE

N = 38 (study completers of the “Peripheral induction of inhibitory brain circuits to treat Tourette’s: pilot” study, which was powered to have 32 study completers with up to 38 participants screened)

Power considerations

As this study is an exploratory study to determine the viability of this type of therapy in the real world setting, the sample size was chosen for convenience to include only completers of the MNS pilot study. However, a sample size of 32 provides 75% power to detect improvement of -25% in tic severity or frequency ratings (one tailed). A change of -25% in YGTSS total tic scores is considered clinically meaningful [17].

INCLUSION CRITERIA

Inclusion criteria for all participants:

- Completed participation in the study called “Peripheral induction of inhibitory brain circuits to treat Tourette’s: pilot”
- Informed consent by adult participant; assent by child and informed consent by guardian

EXCLUSION CRITERIA

Exclusion criteria for all subjects:

- Has an implanted device that could be affected by electrical current
- Pregnancy known to participant or (for children) to the parent
- Severe or unstable systemic illness
- Factors (such as exaggerated symptom report) that in the judgment of the principal investigator may make the outcome measures inaccurate
- Judged by investigator to be unlikely to complete study procedures

Additional exclusion criteria were required for participation in the RCT.

CONCOMITANT MEDICATIONS

Required: none

PROHIBITED MEDICATIONS

none

TREATMENTS AND DOSAGE

TENS stimulation

- The device (TENS-7000) was judged by the FDA to be substantially equivalent to similar approved devices in the “Transcutaneous electrical nerve stimulator for pain relief” category, 501(k) premarket notification number [K080661](#).
- 12 Hz square-wave, 200 μ s pulses will be delivered over the median nerve at the wrist at the threshold for thumb movement to surface electrodes (conductive gel, 30 mm apart center-to-center, anode distal).
- The participant will determine the current delivered, using an analog knob on the TENS unit. We instruct them that we believe the stimulation has to cause thumb movement in order to be effective (based on the Nottingham EEG results), so they will likely need to adjust the current delivered each time they turn it on, given expected fluctuations in actual current delivery with changes in electrode position or electrode-skin resistance throughout the day.
- Participant can choose right or left median nerve (we will suggest their nondominant hand to minimize interference with daily activities).
- Participant will determine duration and timing of stimulation.

ANALYSIS PLAN/APPROACH/METHODOLOGY

Outcome measures

The primary outcome measures are derived from the surveys administered online throughout the study period. Surveys completed when the stimulator is turned on will assess the tic frequency and intensity prior to stimulation. For surveys where the stimulator is currently on or was recently turned off, the tic frequency and intensity will be reported in addition to discomfort and overall symptom relief. The time of each survey will be recorded in order to determine how long the device was on and the relative timing of each survey. Analysis can begin for each participant after their final survey has been completed.

Primary Outcome Measures:

1. Time spent using the device (minutes per day and number of days per week used over four-week period)
2. Do you expect to continue to use the stimulator? (yes/no/maybe, at study conclusion)
3. Comparison of tic frequency between “turning ON” and “turning OFF” surveys (scale of 0-5)
4. Comparison of tic intensity between “turning ON” and “turning OFF” surveys (scale of 0-5)
5. Mean discomfort while using stimulator (scale of 0-3 adapted from the CGI-I Efficacy Index)
6. Relationship to blinded study results (correlation of change in tic frequency and intensity during this study as in outcome measures 3 and 4 above with change in tic frequency and intensity respectively during active, rhythmic stimulation during the RCT).

Secondary Outcome Measures:

1. What was the overall impact of the stimulation on symptoms throughout the study period? (CGI-Efficacy index)
2. How much discomfort did the stimulation cause throughout the study period? (CGI-Efficacy index)
3. Average therapeutic effect while using stimulator
4. Comparison of tic severity prior to and at the end of the study

5. Check whether reported symptom improvement across different stimulation sessions was influenced by stimulation intensity or reported discomfort
6. Comparison of tic frequency between “more than 60 minutes after turning off stimulator” and “less than 60 minutes after turning off stimulator”
7. Comparison of tic intensity between “more than 60 minutes after turning off stimulator” and “less than 60 minutes after turning off stimulator”
8. “How long do you think the improvement in your tics lasted after you turned off the device?”
9. Compare participants’ perception of tic improvement from post-study survey to their results collected during the study
10. Compare participants’ perception of length of tic improvement after turning off the stimulator from post-study survey to their results collected during the study
11. Do certain participant characteristics predict who will be “responders”?
12. Qualitative analysis of open-ended questions

Data analysis

Data storage, sharing and management. Survey data, which **will not contain PHI**, will be collected and stored on Google Forms. This data will be shared on the [Open Science Framework](#).

Overall statistical approach. To prevent “HARKing” (hypothesizing after results are known) [20], we have **registered our hypotheses** and analysis strategy on [OSF.io](#) prior to initiating enrollment. For this pilot study, all statistical tests will be reported independently, with a warning about multiplicity of tests. However, we limit the number of primary outcome measures.

Aim 1 (determining real-world utility of stimulation). Descriptive data regarding the duration of use of the device will be reported as the mean and standard deviation of minutes per day, as well as the mean number of days used per participant. Answers to the question, “if you had a free stimulator, would you continue to use it after the study finishes?” will be reported as percentages answering “yes,” “no,” and “maybe.” Additionally, a summary of common themes to the open-ended questions about the device will be reported.

Aim 2 (determining momentary self-rated efficacy and side effects of stimulation). Comparisons of tic frequency and intensity ratings immediately prior to and following use of the simulator will be reported as paired t-tests. A similar analysis will be completed for ratings of frequency and intensity made less than 60 minutes after turning off the stimulator vs. more than 60 minutes after turning off the stimulator (unpaired t tests). Average discomfort and average therapeutic effect while using the stimulator will be reported descriptively as percentage of participants choosing each rating. A similar analysis will be conducted on average discomfort and average therapeutic effect over the entire study period as reported in the final survey. Additionally, the discomfort and therapeutic ratings collected throughout the study will be compared with those taken at the end of the study. Participants’ scores on the ATQ (adult tic questionnaire) and PUTS scale (premonitory urge for tic scale) before and after the study will be compared using the paired t-test. Participants’ responses to the question “How long do you think the improvement in your tics lasted after you turned off the device?” will be reported as percent of participants choosing each option, and these perceptions will be compared with their numerical ratings throughout the study. Finally, we will determine if certain factors have a significant impact on who is a “responder” to the device, as measured by those participants with a greater than 25% reduction in tic frequency or intensity during stimulation. The factors to be examined include

age, sex, baseline YGTSS, complex tics ever, phonic tics ever, baseline ADHD severity, and baseline OCD severity.

Aim 3 (Compare results of trial with those from “Peripheral induction of inhibitory brain circuits to treat Tourette’s: pilot”). Both changes in tic frequency and tic intensity will be compared between the RCT and the open-label study using correlation analysis. The change observed in the RCT will be plotted on the x-axis, and the change observed in the open-label study will be plotted on the y-axis. A line of best fit will be generated to determine if there is a significant relationship between the two, and if so, in what direction it occurs.

Additional analysis details. Outliers will be determined at the level of the individual variables before the main analyses. If the distribution clearly deviates from a normal distribution on visual inspection because of outlying values, after transformation if appropriate, we will use a nonparametric analysis.

SAFETY MONITORING

We anticipate no adverse events other than possible mild, transient discomfort related to the stimulation. However, we will report any adverse events to the Institutional Review Board according to its regulations, including an annual summary.

No serious adverse events (SAEs) are expected. The PI will monitor for unanticipated problems, life-threatening events or deaths. If contrary to expectations any SAE occurs that the investigator considers possibly, probably or definitely related to participation in the study, we will confer with the IRB before continuing enrollment.

REFERENCES CITED

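### Participants pick the on or off text survey by the stimulator state when the text arrives, so a late answer can go on a form that does not match the moment rated

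*Combined protocol and SAP*

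**What the plan says.** Under *Online during study period*, the protocol lists four survey occasions: (a) switching the stimulator on, (b) switching it off, (c) answering a text with it on, and (d) answering a text with it off. For the texts it says "Texts will be sent twice daily at predetermined times", and that the participant uses c or d "depending on stimulator use when the text is received". The two forms are headed "Answering a text, stimulator currently on" and "Answering a text, stimulator currently off". Form c asks for tic intensity, tic frequency, discomfort and overall improvement. Form d asks only for tic intensity and frequency. No expiry or late-answer rule is given, there or in the analysis plan.

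Under *Objectives*, the second purpose of the study is to "determine momentary self-rated efficacy and side effects of stimulation".

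Under *Outcome measures*, "The time of each survey will be recorded in order to determine how long the device was on and the relative timing of each survey". The text does not say whether that time is receipt of the text, opening of the form or submission.

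Under *Data analysis*, Aim 2, the after-effect comparison sets "ratings of frequency and intensity made less than 60 minutes after turning off the stimulator" against those made later than that, using unpaired t tests.

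**The concern.** A momentary rating needs three things to refer to the same instant: the state label, the tics being rated and the time stamp. Here the label is tied to receipt, while the form headings and the intent of Aim 2 point to the moment of answering. The two agree only if the reply is prompt or the device has not been switched in between. Participants are free to start and stop stimulation as they like, and nothing limits how late they may reply, so disagreement is possible in both directions.

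The texts are the only in-study ratings not triggered by switching the device. Form c can contribute to mean discomfort during use (primary outcome 5) and to average therapeutic effect during use (secondary outcome 3). Form d supplies ratings away from the switching times for the 60-minute comparisons (secondary outcomes 6 and 7). A wrong form matters beyond its label: because d lacks two of c's items, choosing d for a moment of stimulation means that those two ratings are never collected.

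**Working it through.** The plan states no figure on this point, so there is none to reproduce. The check has three steps.

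**1. Follow the rule in each direction.**

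| Device at receipt | Device at answering | Form under the stated rule | Form matching the moment rated | Consequence |
|---|---|---|---|---|
| On | On | c | c | None |
| Off | Off | d | d | None |
| On | Off | c | d | Discomfort and improvement are asked about an unstimulated moment, but can enter primary outcome 5 and secondary outcome 3 |
| Off | On | d | c | Discomfort and improvement are not asked; a stimulated tic rating can enter secondary outcomes 6 and 7 |

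**2. Check the 60-minute window.** Suppose a text arrives at 12:00 with the device on, the device is switched off at 12:20, and the answer is given at 13:40. The answer comes 13:40 − 12:20 = 80 minutes after switch-off. Aim 2 sorts ratings by when they are made, so a momentary rating timed at completion belongs in the later group, and its time stamp puts it there. On that reading the window error is 0% at any delay.

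An error from timing alone would need a rating that describes the moment of receipt but carries a completion time. In that case, for texts received uniformly over the first 60 minutes after switch-off and answered after a delay D, the share crossing the cut is min(D, 60)/60. This is 5/60 = 8%, 10/60 = 17% and 30/60 = 50% for delays of 5, 10 and 30 minutes. The documents do not describe such a rating.

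What remains is the label. The 13:40 answer is on form c, and the plan does not say whether form c answers given after switch-off enter the comparison or are left out.

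**3. Illustrate how often form c would be wrong.** The documents give the number of texts: 2 per day × 28 days = 56 per participant. The window of ± 5 days gives 2 × 23 = 46 to 2 × 33 = 66. That is 56 × 32 = 1,792 texts for 32 participants, or 56 × 38 = 2,128 for 38. These are scheduled texts. The share arriving during a session is unknown.

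Delay D and session length S are assumptions. If receipt is uniform over the session and D is fixed, the share of form c texts answered after switch-off is min(D, S)/S:

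| Session length S | D = 5 min | D = 10 min | D = 30 min |
|---|---|---|---|
| 30 min | 5/30 = 17% | 10/30 = 33% | 30/30 = 100% |
| 60 min | 5/60 = 8% | 10/60 = 17% | 30/60 = 50% |
| 120 min | 5/120 = 4% | 10/120 = 8% | 30/120 = 25% |

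These are shares of form c texts whose state has changed by the time of answering. They do not measure bias in any outcome. The reverse case (d answered during a session) depends on how soon the next session starts, which cannot be derived from the documents.

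**The case against.** The best defence is that the form headings already speak of the current state, and *Outcome measures* uses similar language, so a sensible participant would answer for the present moment. The survey wording that participants see is not in the documents. This shows that the intent was probably right, but the one explicit instruction on choosing a form says otherwise, and a participant who follows it exactly goes wrong.

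The second defence is the time stamps. The switching-on and switching-off surveys bracket each session, so the true state at any answer can be worked out whichever form was used. That stands in part. It needs those surveys to be complete, and the protocol itself foresees compliance reminders. It also cannot recover items that form d never asked.

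Third, discomfort is also collected at every switch-off, and a late form c still reports on a session that took place. This limits the effect on primary outcome 5 but does not remove it, since a recollection is not a reading taken during use. The recall period of the items is not shown.

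A reader might infer three stronger things.

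- **Late answers fall in the wrong 60-minute window.** Step 2 of the working shows that this does not follow for a momentary rating timed at completion.
- **The mislabelling blurs the main tic comparison.** Primary outcomes 3 and 4 use the surveys at switching on and off. Primary outcome 6 correlates those same changes with the earlier trial. No planned analysis compares form c with form d.
- **Participants will wait to answer until their tics are calm.** Nothing in the documents supports this.

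**Conclusion.** The point holds as a minor flaw in a stated rule. The instruction on choosing a form conflicts with the form headings and with the momentary purpose of the ratings, and nothing limits late replies. Its reach is primary outcome 5 (as far as form c discomfort ratings are used) and secondary outcomes 3, 6 and 7, in a study that calls itself exploratory.

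The size cannot be fixed from the documents. Over the assumed delays of 5 to 30 minutes and sessions of 30 to 120 minutes, between 4% and 100% of form c texts would be answered after switch-off, so the illustration shows mainly that the answer depends on unknown behaviour. With prompt replies the problem disappears. It would be wrong to state as fact that ratings will be misfiled, or that the time of each survey is the completion time: the latter is the natural reading but is not written down.

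**What to change.** Change the instruction so that the participant chooses c or d by the stimulator state at the moment of answering, and rates tics at that moment. This brings the rule into line with the headings, and it makes sure that discomfort and improvement are asked whenever the device is on. It should be done before data are collected, because items missing from form d cannot be recovered later.

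Add to the analysis plan:

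- The survey time is the completion time.
- State and 60-minute window are assigned from that time, checked against the switching-on and switching-off surveys, whatever form was used.
- The text send time is kept and linked to the answer, so that late answers can be examined in a sensitivity analysis.

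The cost is one changed phrase, a few SAP sentences and a little more data checking. A fixed cut-off, such as excluding answers more than 30 minutes after the text, is optional. Once form, rating and time refer to the same moment, late answers are correctly classified, and a cut-off would discard usable data.

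### Primary outcome 6 uses only the RCT's active-stimulation change, so a significant laboratory-home correlation cannot tell device benefit that carries over from a non-specific response shared by both settings

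*Combined protocol and SAP*

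**What the plan says.** Primary Outcome Measures, item 6, is labelled as a relationship to the results of the blinded study. Its home variable is given as "correlation of change in tic frequency and intensity during this study as in outcome measures 3 and 4 above", that is, the change in self-ratings on 0-5 scales between the surveys at switching on and switching off. Its RCT variable is the "change in tic frequency and intensity respectively during active, rhythmic stimulation during the RCT".

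The Aim 3 paragraph under Data analysis is less specific: "The change observed in the RCT will be plotted on the x-axis". It does not repeat that only active stimulation is meant. The decision rule there is "A line of best fit will be generated to determine if there is a significant relationship between the two".

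Objectives gives the purpose of using both studies: "in order to compare laboratory and real-world efficacy". Aim 3 there adds that "Participants in this study are drawn from completers of the 'peripheral induction' blinded RCT". First visit, item 2, provides that all data from that "study will be imported for comparison with information collected during this study".

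No section subtracts, adjusts for or separately correlates the RCT control condition. The documents also do not say what that condition was, who rated tics in the RCT, whether its design was crossover or parallel, or from what reference point its change is measured.

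**The concern.** A blinded, controlled study adds one thing to an open-label one: the response beyond the control condition. The change under active stimulation alone contains any device effect together with any non-specific response. The home change is open-label and self-rated, by participants who are told (Treatments and dosage) what the investigators believe makes stimulation effective, so it contains both as well.

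If part of the non-specific response is a stable trait of the person, it enters both axes and correlates them. A positive slope could then mean that device benefit carries over from laboratory to home, or only that the same people improve, or report improvement, in both settings. Aim 3 is meant to compare efficacy in the two settings, and the results are to inform a later controlled trial, so the difference matters.

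**Working it through.** **The plan's own figure.** The only power figure (Sample size) is 75% to detect a 25% improvement with 32 participants, one-tailed. It concerns the rating change, not outcome 6. No SD or alpha is given, so it can only be inverted: at one-sided 0.05 with a paired t test it implies a standardised change of 0.419, hence an SD of change of 25/0.419 = about 60%. No figure is given for the correlation.

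**Inputs.** n = 32, the completers for which the RCT was powered (38 as an alternative). Alpha is not stated; two-sided 0.05 is assumed. The critical correlation is t/√(n − 2 + t²) = 2.042/√(30 + 4.17) = 0.349; at n = 38 it is 0.320.

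**Model.** Each change score has variance 1.
- Home change: y = P + T + e
- RCT active change: xₐ = P + T + e
- RCT control change: x_c = P + e

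P is the stable non-specific response with variance share s, T is a device effect shared by laboratory and home, and each e is independent. Unshared fluctuation, including waxing and waning of tics at separate times, belongs in e and creates no correlation. Each setting was simulated 40,000 times.

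**No device link (T = 0), equal share s in both settings.** The expected active-only correlation is about s, and the expected correlation of y with xₐ − x_c is 0.

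| Share s | Mean active-only r | Significant, n = 32 | Significant, n = 38 | Significant, difference score, n = 32 |
|---|---|---|---|---|
| 0 | 0.00 | 5% | 5% | 5% |
| 10% | 0.10 | 8% | 9% | 5% |
| 20% | 0.20 | 19% | 23% | 5% |
| 30% | 0.30 | 39% | 46% | 5% |
| 40% | 0.40 | 64% | 72% | 5% |
| 50% | 0.49 | 85% | 91% | 5% |

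**Unequal shares.** With 30% at home and a smaller share in the laboratory, the expected r is √(s_lab × 0.30). At a 10% laboratory share it is √0.03 = 0.17, and 16% of trials are significant. At 5% the rate is 10%, and at 0% it is 5%.

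**Control evokes only half of P.** The difference score no longer holds 5%. It rejects in about 7, 10, 16 and 26% of trials at s = 20, 30, 40 and 50%, against 19, 39, 64 and 85% for active-only.

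**Price of the difference score when a shared device effect exists.**
- P and T with variance 0.3 each and error 0.7 (total 1.3, so each is 0.3/1.3 = 23%): active-only r = 0.6/1.3 = 0.46, difference r = 0.3/√(1.7 × 1.3) = 0.20. Significant in 78% and 20% of trials.
- P and T at 30% each (error 0.4): active-only r = 0.60, difference r = 0.3/√1.1 = 0.29. Significant in 97% and 36%.
- T at 30% and no P: active-only r = 0.30, difference r = 0.3/√1.7 = 0.23. Significant in 39% and 25%.

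In the first two cases part of the active-only rate is itself due to P.

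**The case against.** The strongest reply is that the plan never claims a device-specific link. It asks whether laboratory and real-world results agree, in an exploratory convenience sample, and setting active laboratory change against active home change is a fair like-with-like description. That stands, and it is why the outcome need not be replaced. It does not settle what a significant slope means when the stated purpose is to compare efficacy.

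A reader might go further and infer that reporting habits are known to drive both axes, or that the correlation is certain to be spurious. The documents do not support this. They do not say that the RCT change was self-rated. If blinded observers rated it, a shared reporting tendency would shrink, although a placebo response in the tics themselves would remain. The size of any shared response is unknown, and at a small laboratory share the inflation is modest.

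A reader might also infer that the difference score should become the primary outcome. That rests on an RCT design the documents do not describe. The score has low power at n = 32, and it removes only non-specific response that is equal in both conditions. If the control was itself a form of stimulation, subtraction would also change the quantity being estimated. In addition, the plan says its analysis strategy was registered before enrolment, which argues for adding to the outcome.

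Two features of the plan might seem to cover the point but do not. The warning about multiplicity concerns the number of tests, not what this one can show. The exclusion for exaggerated symptom report is an investigator's judgement at entry and does not address ordinary placebo response.

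**Conclusion.** The concern holds in a limited form. As defined, primary outcome 6 cannot separate device benefit that carries over from a stable non-specific response present in both settings. Without any device link, such a response alone would make the correlation significant in about 8 to 85% of trials at n = 32 for shares of 10 to 50% in both settings, and less often if the laboratory share is smaller. These rates show what can happen under assumed shares, a two-sided 0.05 test and normal errors; they do not estimate the bias in this trial. The active-only correlation remains valid as a description of whether people who improved under active stimulation in the RCT also report benefit at home. The gap is that the plan neither shows the control-condition comparison nor limits the interpretation.

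**What to change.** 1. Keep the active-only correlation as the primary outcome, and state in both Primary Outcome Measures, item 6, and the Aim 3 analysis that the same RCT variable is meant, with its reference point.
2. Report beside it, for frequency and for intensity: (a) the correlation of home change with the RCT control-condition change, as a negative control; and (b) the correlation of home change with the per-person active-minus-control difference.
3. If the RCT was parallel-group, per-person differences do not exist; compare the correlations by arm instead. With about half of 32 completers in the active arm, the critical correlation there would be about 0.50 (n = 16).
4. State in advance that an active-only correlation of similar size to the control-condition correlation is not evidence that device-specific benefit carries over from laboratory to home, and that a non-significant difference correlation is inconclusive.

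The cost is plan wording and a little more analysis. No new data are needed, since the RCT data are already imported. The limits should be stated with the results: the difference score has low power (about 20 to 36% in the cases above with both kinds of response present) and protects fully only if the control evokes the same non-specific response as active stimulation.
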